1.1 Title

Efficacy and Safety Comparison of Liraglutide, Glimepiride, and Placebo, All in Combination With Metformin, in Type 2 Diabetes. The LEAD (Liraglutide Effect and Action in Diabetes)-2 study (NCT00318461).

1.2 Intended aim(s)

To assess whether the glycemic control achieved by adding liraglutide to metformin was non-inferior to glimepiride and metformin combination therapy after 26 weeks of treatment, in subjects with type 2 diabetes and previously treated with oral antidiabetic therapy.

1.3 Primary endpoint for replication

Long-term glycemic control defined as change in HbA1c from baseline to the end of follow-up.

1.4 Required power for primary endpoint and noninferiority margin (if applicable)

The sample size calculation was based on both HbA1c and body weight endpoints. The assumed standard deviation for HbA1c and the coefficient of variance for body weight were 1.2% and 3%, respectively. The combined power (calculated as the product of the marginal powers for HbA1c and body weight) was at least 85%. Noninferiority of glycemic control with liraglutide versus glimepiride was concluded if the upper limit of the two-sided 95% CI for the treatment difference was < 0.4%.

With a standard deviation of 1.2% for HbA1c and a coefficient of variance of 3% for body weight, it was concluded that at least 168 subjects were required to complete the treatment in the liraglutide and in the glimepiride, respectively. Assuming a dropout rate of 25% after 26 weeks of treatment, the number of subjects to be randomized was calculated to be 228 in each of the liraglutide and glimepiride treatment groups.

1.5 Secondary endpoint for replication (assay sensitivity) and RCT finding n/a

1.6 Trial estimate

The HbA1c mean decreases of 1.0% (\pm 0.1) for both the 1.2 and 1.8 mg/day liraglutide groups and 1.0% (\pm 0.1) for glimepiride group. Treatment difference in HbA1c was 0.0% [95% CI: -0.2 to 0.2] for both comparisons liraglutide 1.2 mg/day versus glimepiride and liraglutide 1.8 mg/day versus glimepiride (Nauck M et al. 2009).

2. Person responsible for implementation of replication in Aetion

[name], MPH, implemented the study design in the Aetion Evidence Platform and SAS 9.4. She is not responsible for the validity of the design and analytic choices. All implementation steps are recorded, and the implementation history is archived in the platform.

[figure not shown]
3. Data Source(s)

Optum CDM

4. Study Design Diagram

The study design diagram visualizes key aspects of the longitudinal study design for expedited review.

Figure 1. Design Diagram - LEAD-2 TRIAL REPLICATION

5. Cohort Identification

5.1 Cohort Summary

This study will involve a new user, parallel group, propensity score-matched, retrospective cohort design comparing injectable subcutaneous liraglutide (1.2 or 1.8 mg/day) to oral glimepiride (4 mg once daily). Treatments in both arms are administered in combination with metformin (up to 2,000 mg/day). Patients will be required to have continuous enrollment during a baseline period of 180 days before initiation of liraglutide or glimepiride. The analyses will be restricted to individuals with type 2 diabetes mellitus who have been previously treated with antidiabetic drugs. In the replication, previous anti-diabetic treatment was defined as the presence of at least 2 prescriptions for metformin within 6 months before and including cohort entry.

5.2 Important steps for cohort formation

New use of liraglutide (exposure) is defined as no use of the exposure drug within 180 days prior to index date. New use of glimepiride (comparator) is defined as no use of the comparator drug within 180 days prior to index date. Eligible patients are required to be new users with respect to both exposure and comparator groups (i.e., no use of both exposure and comparator drugs) within 180 days prior to index date.

5.2.1 Eligible cohort entry dates

Liraglutide indication as an adjunct to diet and exercise to improve glycemic control in adults with type 2 diabetes mellitus was approved by FDA on Jan 25, 2010 (the approval of glimepiride for the same indication was antecedent to 2010). Thus, the initial eligible cohort entry date is the first date after the FDA approval available in the data. The last eligible date is June 30, 2020, three months before the end of all available data in Optum CDM. Since the effects of liraglutide and glimepiride on the outcome (i.e., change in HbA1c) will be estimated between 56 and 212 days after cohort entry (see Section 6.3), this will allow all eligible patients to contribute to the outcome. The database used is Optum CDM because lab results/values are available in this database for a subset of laboratory tests, including the A1C tests. The following eligible cohort entry dates were included:

- Optum CDM: Jan 26, 2010 Jun 30, 2020
- 5.2.2 Specify inclusion/exclusion criteria for cohort entry and define the index date Inclusion and exclusion criteria were adapted from the trial as closely as possible. Definitions for all inclusion/exclusion are provided in **Appendix A** and are summarized in the flowcharts below.

Note. Patients who are censored between cohort entry and the beginning of the outcome assessment window (i.e., 0.x-56 days after cohort entry) for the reasons reported in the Section 6.3.2 will not contribute to the unmatched or matched cohorts. Further details on the number of patients who are excluded from the study cohort are reported in the Section 7.

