6.3.1 Outcome variables

Effectiveness outcome variables of interest (definitions provided in **Appendix A**):

• **Primary outcome:** Changes in HbA1c from baseline to 26 weeks of treatment (end of follow-up).

Note. In the trial, HbA1c was also measured at 8, 12, 18 weeks (± 3 days) after randomization. Missing values of HbA1c at 26 weeks were replaced using last observation carried forward (LOCF) in the intention-to-treat (ITT) analysis set. In the replication, HbA1c at baseline will be defined as the last recorded HbA1c value measured within 90 days before and including cohort entry date in both groups. HbA1c at the end of follow-up will be defined as a recorded HbA1c value closest to the end of the 26th week and measured between 56 and 212 days (8-30 weeks) after cohort entry.

Secondary outcome: --

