6.3.2 Primary analysis and study follow-up

As-treated (AT) analysis will be performed as main analysis. The treatment drug will be defined as the index drug assigned on the day of cohort entry. Patients will be followed for about 30 weeks (212 days). Compared to the trial (Nauck M et al. 2009), we will

extend the follow-up and the outcome assessment periods of 4 weeks. The follow-up and outcome assessment window will start 56 days after cohort entry date and will continue until the earliest date of the following events:

- The first occurrence of the outcome of interest (measured between 56 and 212 days after cohort entry),
- The date of end of continuous registration in the database (disenrollment or end of available data),
- End of the study period,
- Measured death event occurs,
- Index drugs discontinuation (liraglutide, glimepiride or metformin),
- Crossover or addition of drug from the other treatment group,
- Addition of any other anti-diabetic medications,
- Nursing home admission
 - Nursing home admissions are considered a censoring event because the data sources utilized typically provide little to no data on a patient, particularly on drug utilization, after admission. We will utilize this as an exclusion reason for cohorts for the same reason.

Note. To decrease the incidence of missing values of the outcome (specifically, missing of HbA1c values measured between 56-212 days after cohort entry), we required that the eligible patients had at least 3 HbA1c measurements recorded within 365 days before and including cohort entry. This will increase the probability of including in the final cohort patients who are adherent to a routinely HbA1c testing and, consequently, will decrease the frequency of missing values of the outcome. Multiple imputation will be used to handle missing values in the primary analysis, while complete case analysis will be applied in a sensitivity analysis.

7. Initial Feasibility Analysis

Aetion report name:

For liraglutide vs. glimepiride

Optum CDM (continuous HbA1c outcome) https://bwh-dope.aetion.com/projects/details/1688/rwrs/71723

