• Stop analyses until feasibility and power are reviewed by primary investigators and FDA. Reviewers evaluate the results of the analyses described above in Sections 7 and 8, including numbers of patients, patient characteristics, follow-up time, and reasons for censoring by treatment group, as well as overall rates of outcomes and study power. These parameters are re-evaluated and reported in the subsequent sections, after incorporating feedback and refining the protocol.

o Optum CDM

Non-inferiority Analysis	
Standard deviation of outcome	1.01
Non-inferiority limit	0.4
Alpha (2-sided)	0.05
Power (1-beta)	90%
Sample size required per group	110
Total sample size required	220
Number of patients matched	752
Reference	376
Exposed	376

• Stop analyses until feasibility and power are reviewed by primary investigators, FDA, and assigned members of advisory board.

Reviewed by PI:	[name]	Date reviewed:	07/16/2021
Reviewed by FDA:	[name]	Date reviewed:	08/2/2021
Reasons for stopping			
analysis (if required):			

9. Balance Assessment

For liraglutide vs. glimepiride

Optum CDM: see file LEAD-2_programming_steps and output of "STEP 3 - BALANCE Assessment (with dummy outcome) - Paragraphs 9-10 of the protocol"

Date conducted: 06/16/2021

After review of initial feasibility and power analyses, complete creation of the remaining covariates from Section 6.2. Again, using the dummy outcome of a 90-day gap in database enrollment, complete a 1:1 PS-matched analysis. The PS should include the complete list of covariates.

• Provide plot of PS distributions stratified by treatment group.

Note- Please refer to Appendix B.

• Report covariate balance after matching.

Note- For Table 1, please refer to **Appendix B**.

• Report reasons for censoring by treatment group.

	Overall (n. 746)	Liraglutide – exposure (n. 373)	Glimepiride – comparator (n. 373)
Outcome (dummy)	0 (0%)	0 (0%)	0 (0%)
Death	0 (0%)	0 (0%)	0 (0%)
Start of an additional exposure	9 (1.2%)	6 (0.8%)	3 (0.4%)
End of index exposure	194 (26.0%)	137 (18.4%)	57 (7.6%)
Maximum follow-up time	340 (45.6%)	137 (18.4%)	203 (27.2 %)
End of patient data	5 (0.7%)	3 (0.4%)	2 (0.3%)
End of patient enrollment	61 (6.3%)	25 (3.4%)	36 (4.8%)
Start of additional antidiabetic drugs + Nursing home + Metformin discontinuation with allowed 60 days gap	137 (18.4%)	65 (8.7%)	72 (9.7%)

• Report follow-up time by treatment group.

Median Follow-Up Time (Days) [IQR]			

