	Exposure: Liraglutide s.c. 0.6 mg/day, 1.2 mg/day and 1.8 mg/day in combination with metformin (1500-2000 mg/day) for 26 weeks Reference for non-inferiority: Glimepiride (4 mg/day) in combination with metformin (1500-2000 mg/day) Reference for superiority: Metformin monotherapy (1500-2000 mg/day) Aim: To evaluate whether the effect on glycaemic control (as measured by change in HbA1c) of treatment with 0.6 mg/day, 1.2 mg/day and 1.8 mg/day of liraglutide in combination with metformin was superior to metformin monotherapy and non-inferior to metformin and glimepiride combination therapy after 26 weeks of treatment.	Exposure: new-use of Liraglutide (washout 180 days) in combination with metformin NDC Generic Name: LIRAGLUTIDE NDC Brand name: Viktoza (FlexPen) Reference: new use of Glimepiride (washout 180 days) in combination with metformin NDC Generic Name: GLIMEPIRIDE NDC Brand name: GLIMEPIRIDE AMARYL		Criteria
	PRIMA	RY OUTCOME		Adequate mapping in claims
	Change in HbA1c from baseline to week 26 Note: in the trial missing values are replaced with last value carried forward [LVCF]	Measured as change in HbA1c from baseline to the last recorded HbA1c value between 56 and 212 days after drug initiation: Loinc codes: 17855-8, 17856-6, 41995-2, 43150-2, 4548-4, 4549-2, 55454-3, 71875-9, 74246-0		Intermediate mapping in claims
	INCLUS	SION CRITERIA		Poor mapping or cannot be measured in claims
0	Informed consent obtained before any trial-related activities (trial-related activities are any procedure that would not have been performed during normal management of the subject).	N/A		Can't be measured in claims but not important for the analysis
1	(1.1) Subjects diagnosed with type 2 diabetes and (1.2) treated with OAD(s) for at least three months.	1.1 Selecting patients with a diagnosis of type 2 diabetes measured from the time of enrollment to the day of drug initiation inpatient (any position), outpatient (any position): Type 2 diabetes: 1.1 Selecting patients with at least two prescriptions of metformin within 183 days before cohort entry (OADs treatment ≥ 3 months), and 1.3 Concomitant or current use of metformin at cohort entry date in both treatment groups: Generic name: Metformin Hel 1.4 Selecting patients with no other anti-diabetic treatments within the 180 days before cohort entry:		

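### Does closing cohort entry three months before the end of data leave late entrants too little follow-up for a week-26 HbA1c?

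*Combined protocol and SAP*

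**What the plan says.** Section 5.2.1 runs entry from January 26, 2010 to June 30, 2020: "The last eligible date is June 30, 2020, three months before the end of all available data in Optum CDM". It notes that the outcome is estimated between days 56 and 212, and concludes that "this will allow all eligible patients to contribute to the outcome".

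Section 6.3.1 defines the follow-up measurement as the "recorded HbA1c value closest to the end of the 26th week and measured between 56 and 212 days (8-30 weeks) after cohort entry". The primary-outcome row of Appendix A instead takes the "last recorded HbA1c value between 56 and 212 days after drug initiation". Section 6.3.2 follows patients to about day 212, stopping at the earliest of several events. These include the first in-window outcome and the end of available data. Missing outcomes are multiply imputed in the primary analysis, with complete cases as a sensitivity analysis.

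End-of-data censoring is tabulated by arm in Section 7 (feasibility run) and Section 9 (matched run with a dummy outcome). The results shell in Section 14.3 has the same row.

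**The concern.** Section 5.2.1 cites the whole 56-to-212-day window, but a gap of about 92 days secures only its first part. The last entrant has 36 of the 156 window days, all of them well before week 26.

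If the outcome is the value nearest to week 26, or the last one in the window, a late entrant's week-8-to-13 value stands in for a week-26 value. Imputation leaves observed values alone, so it would not correct this. If the treatment difference changes between weeks 8 and 26, the non-inferiority estimate would be pulled towards its early value. The calendar-period covariate in Appendix B has a last band of 912 days (January 2018 to June 2020), too wide to isolate the final months of entry.

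**Working it through.** **1. Dates.** The plan's three months is taken as June 30 to September 30, 2020 = 92 days.

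- Against day 56: 92 − 56 = 36 days of window are secured, out of 212 − 56 = 156.
- Against week 26: 182 − 92 = 90 days short, so entrants after about April 1, 2020 cannot reach day 182.
- Against day 212: 212 − 92 = 120 days short, so entrants after about March 2, 2020 have a shortened window.

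The plan's statement that every eligible patient can contribute holds, because 92 exceeds 56.

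**2. Patients affected if follow-up stops at the first in-window value (Section 6.3.2).** The cut-off then changes only patients who reach the end of data without an HbA1c. Section 7 gives 37/3,470 = 1.1% (printed as 1.0%): 3/378 = 0.8% on liraglutide and 34/3,092 = 1.1% on glimepiride. Their outcomes are missing and are imputed.

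**3. Patients with a shortened window in the matched cohort.** The dummy-outcome run in Section 9 (373 per arm) does not stop at an HbA1c, so it shows this most directly. With even entry over the last 120 days,

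end-of-data censorings = (patients with a shortened window) × (mean share still followed over days 92 to 212).

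The share still followed is interpolated linearly from the printed quartiles and the maximum-follow-up counts.

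- Liraglutide: 0.75 at day 89, 0.50 at day 150, 137/373 = 0.367 at day 212. The value at day 92 is 0.738. Mean = [58 × (0.738 + 0.50)/2 + 62 × (0.50 + 0.367)/2] / 120 = 0.523. Then 3/0.523 = 5.7 patients.
- Glimepiride: 1.00 at day 56, 0.75 at day 119, 203/373 = 0.544 at day 212. The value at day 92 is 0.857. Mean = [27 × (0.857 + 0.75)/2 + 93 × (0.75 + 0.544)/2] / 120 = 0.682. Then 2/0.682 = 2.9 patients.
- Total: 8.7/746 = 1.2%. The exact Poisson 95% interval for 5 events is 1.62 to 11.67, which scales to 2.8 to 20.2 patients (0.4 to 2.7%).

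**4. Larger figures, and whether they fit.** The same method on the Section 7 run gives mean shares of 0.220 and 0.283, hence 3/0.220 + 34/0.283 = 13.6 + 120.1 = 134 of 3,470 (3.9%; 3.6% liraglutide, 3.9% glimepiride). Uniform entry gives 3,474 × 120/3,809 = 109 (3.2%) over the whole period, or 1,369 × 120/912 = 180 (5.2%) at the 2018–2020 rate in Appendix B.

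Applied to the matched cohort with the shares from step 3, these predict the following end-of-data censorings, against 5 observed:

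| Assumption | Expected | Poisson P(5 or fewer) |
|---|---|---|
| Uniform entry, whole period | 373 × 120/3,809 × (0.523 + 0.682) = 14.2 | 0.005 |
| 3.6% and 3.9% by arm | 373 × (0.036 × 0.523 + 0.039 × 0.682) = 17.0 | 0.0007 |
| 2018–2020 entry rate (4.3% and 5.3% by arm) | about 22 | 0.00002 |

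So the matched-cohort counts support about 1.2%, not 3 to 5%.

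**5. Effect on the estimate.** Shift = share affected × change in the treatment difference between weeks 8–13 and week 26. The documents give no time course, so a change of 0.1 to 0.5 points is assumed.

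- At 1.2%: 0.012 × 0.1 to 0.012 × 0.5 = 0.001 to 0.006.
- At the upper limit of 2.7%: 0.027 × 0.5 = 0.014.
- At 5.3%, the upper Poisson limit of the Section 7 estimate: 0.053 × 0.5 = 0.027, or 7% of the 0.4 margin.

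These figures err high, because they treat every shortened window as a changed outcome. A patient cut off at day 200 can still supply a week-26 value.

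**The case for a change.** The best case for acting is that the remedy is cheap and the comparative analysis in Section 13 is still blank. One sentence and a count by arm would tell readers that only day 56 is secured. A sensitivity analysis excluding entrants with fewer than 212 days to the end of data would use a criterion fixed at entry, so it would not condition on follow-up. The end-of-data rows miss entrants whose short window ended for another reason or who already had an early value. Complete-case analysis keeps patients whose only value is early.

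The factual part of this stands: the end-of-data date is not printed and no count of shortened windows is planned. The end-of-enrollment row (61 of 746 in Section 9) may also hold some of these patients, so 1.2% could be low.

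The call for change does not follow. A value from day 56 onward is valid under the plan's own definition, and Section 6.3.1 notes that the trial carried earlier values forward. Dropping about 6 of 373 liraglutide users would leave the estimate where it was. Moving the entry date would discard some patients with valid outcomes and require a new flowchart and match after reviews already dated July and August 2021.

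Whether an early value becomes the outcome at all depends on which of the closest, first and last rules applies. That inconsistency between Section 6.3.1, Section 6.3.2 and Appendix A is a separate matter, and moving the entry date would not settle it. The first-value rule also bears on timing far more than the cut-off does: median follow-up in Section 7 is 99 days.

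**Conclusion.** No change is needed. The gap secures day 56 and not week 26, but Section 5.2.1 claims only that everyone can contribute an outcome, and that is true. What is missing is reporting detail that analysts can supply from the data. The choice of date is a fair trade-off between keeping recent initiators and giving all of them the full window.

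About 1.2% of the matched cohort (0.4 to 2.7%) have a shortened window, with no arm imbalance shown on very few events (3 against 2). The expected shift is 0.001 to 0.006 points, and 0.027 at the most pessimistic figure considered, against a margin of 0.4. The cut-off alone is therefore unlikely to alter the non-inferiority conclusion.

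This rests on data ending about September 30, 2020, even entry within the last 120 days, late entrants being censored like the rest, linear interpolation between the printed quartiles, and the assumed 0.1 to 0.5 point change in treatment difference.

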5.3 Flowchart of the study cohort assembly

For liraglutide vs. glimepiride: Aetion link: https://bwh-dope.aetion.com/cohorts/details/23482/1688/71700

	Optum	
	Excluded Patients	Remaining Patients
All patients		79,335,559
Did not meet cohort entry criteria	-78,554,666 (99%)	780,893
Excluded due to insufficient enrollment	-119,528 (15%)	661,365
Excluded due to prior use of referent	-424,186 (64%)	237,179
Excluded due to prior use of exposure	-138,679 (58%)	98,500
Excluded because patient qualified in >1 exposure category	-85 (<1%)	98,415
Excluded based on nursing home admission in the prior 180 days	-3,784 (4%)	94,631
Excluded based on gender missing or unknown	-10 (<1%)	94,621
Excluded based on Inclusion #1.1 - Type 2 diabetes mellitus	-6,027 (6%)	88,594
Excluded based on Inclusion #1.2 - Metformin use (2 prescriptions within 183 days)	-55,832 (63%)	32,762
Excluded based on Inclusion #1.3 - Concomitant initiation or concurrent use of metformin	-3,670 (11%)	29,092
Excluded based on Inclusion #1.4 - No use of other anti-diabetic meds	-9,861 (34%)	19,231
Excluded based on Inclusion #2.1 - 3 records of HbA1c 2-20% values/results within 365 days	-13,962 (73%)	5,269
Excluded based on Inclusion #2.2 - At least 1 lab value HbA1c 7-11% recorded within 90 days	-808 (15%)	4,461
Excluded based on Inclusion #3.1 - Age > 18	-0 (<1%)	4,461
Excluded based on Inclusion #3.2 - Age < 80	-87 (2%)	4,374
Excluded based on Exclusion #1 - Morbid Obesity BMI > 40	-147 (3%)	4,227
Excluded based on Exclusion #2 - Any insulin use	-234 (6%)	3,993
Excluded based on Exclusion #3 - End-stage liver disease	-9 (<1%)	3,984
Excluded based on Exclusion #4 - Viral Hepatitis B and C	-7 (<1%)	3,977
Excluded based on Exclusion #5 - CKD stage 5, End-stage renal disease, dialysis, or renal transplant	-0 (<1%)	3,977

Excluded based on Exclusion #6.1 - Myocardial Infarction	-1 (<1%)	3,976
Excluded based on Exclusion #6.2 - Heart Failure	-1 (<1%)	3,975
Excluded based on Exclusion #7 - Anti-VEGFi OR Photocoagulation	-5 (<1%)	3,970
Excluded based on Exclusion #8 - Uncontrolled hypertension	-34 (<1%)	3,936
Excluded based on Exclusion #9 - Malignant neoplasm (except non-melanoma skin cancer)	-79 (2%)	3,857
Excluded based on Exclusion #10 - Recurrent Hypoglycemia	-8 (<1%)	3,849
Excluded based on Exclusion #11 - Systemic glucocorticoids use	-48 (1%)	3,801
Excluded based on Exclusion #12 - Drug addiction or alcohol abuse and dependence	-11 (<1%)	3,790
Excluded based on Exclusion #13 - Mental incapacity, unwillingness to comply	-13 (<1%)	3,777
Excluded based on Exclusion #14 - Pregnancy	-0 (<1%)	3,777
Excluded based on Exclusion #15.1 - Type 1 diabetes mellitus (contraindication glimepiride)	-10 (<1%)	3,767
Excluded based on Exclusion #15.2 - Diabetic ketoacidosis (contraindication glimepiride)	-2 (<1%)	3,765
Excluded based on Exclusion #15.3 - Other metabolic acidosis (contraindication glimepiride)	-1 (<1%)	3,764
Excluded based on Exclusion #16 - Multiple endocrine neoplasia type 2 (MEN2)	-0 (<1%)	3,764
Final cohort		3,764

6. Variables

6.1 Exposure-related variables:

Study drug:

New initiation of injectable subcutaneous liraglutide (1.2 or 1.8 mg/day), a glucagon-like peptide-1 receptor agonist. New initiation is defined as no use of liraglutide within 180 days before treatment initiation (washout period). New users of liraglutide are not allowed to receive glimepiride within 180 days prior to treatment initiation. Concurrent use of metformin is required (2,000 mg/day).

Comparator agent:

New initiation of oral glimepiride (4 mg once daily). New initiation is defined as no use of glimepiride within 180 days before treatment initiation (washout period). New users of glimepiride are not allowed to receive liraglutide within 180 days prior to treatment initiation. Concurrent use of metformin is required (2,000 mg/day).

6.2 Preliminary Covariates:

- Age
- Gender
- Combined Comorbidity Index (CCI), measured over the baseline covariate assessment period, defined as 180 days prior to and including index date.

Covariates listed above represent only a small subset of covariates that will ultimately be controlled for in the design and analysis. We use the covariates above only for initial feasibility analyses to judge whether there is likely to be sufficient overlap between treatment groups to proceed with the study. Remaining covariates are defined only after the study has passed the initial feasibility analysis and the initial power assessment and are listed in Table 1 (Appendix B).

6.3 Outcome variables and study follow-up:

